## 2 Research Methods

### 2.1 Overview of methods

This evaluation will be a mixed methods observational design with mainly descriptive and exploratory analysis. The desk research will review documents, secondary data public available (such as NFHS), and any App background data (deidentified) to better understand the programme.

This is followed by qualitative surveys for which 40 in-depth interviews of various beneficiaries and programme stakeholders (demand creators, service providers, lifestyle partners) will be conducted in person or over phone.

Depending on the insights, we will develop a structured quantitative questionnaire and administer the in-person survey to approx. 480 beneficiaries of SRH and MCH services (total). These surveys will seek information on knowledge, practices, barriers, enablers for SRH and MCH services, exposure o Tiko platform, and how it helped or did not help. The survey participants will be women (18-35years of age) who had subscribed to Tiko card between 2018 and 2020. A subset of these would be regular users, a subset will be sporadic

or one-time user and remaining will be 'non-users'. The sample will try to get adequate representation from all categories.

The in-person surveys will be followed with shorter (10-15 minutes) phone surveys with 1200 active users and 600 non-users who had enrolled on Tiko platform. Phone surveys will collect only basic information needed to confirm findings from in-person and qualitative surveys.

The analysis will triangulate the insights from both qualitative and quantitative analysis. We mainly anticipate descriptive analysis to tabulate indicators related to knowledge, practices, barriers, enablers w.r.t. SRH and MCH services, exposure and use of Tiko platform, how it has helped or not helped or affected their well being, suggestions and preferences for different components of the platform, etc. We anticipate cross tabulation by socio-economic characteristics, regions (say by Cities), and duration of use.

While no analytical tests are anticipated at this time, we expect to conduct standard bivariate tests (t-test and chi2 test) and regression analysis for more nuanced group mean tests or multiple comparison tests (logit, OLS, mixed models). We will be adjusting for standard errors for robust inference. In case of statistical inference, we expect one side test with alpha < 0.1 to consider a relationship or test statistic significant.

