#### 2.2 Sample Design and Power Calculations

For detailed 45-50 minutes in-person surveys, 570 respondents will be interviewed across Rajasthan, Uttar Pradesh and Delhi, of which we expect to complete 480 interviews. This sample size was determined on basis of measuring a proportion of 50% with 5 pp error rate and 95% confidence which yields n of 384 and this n was increased by design effect of 1.25 to account for clustering if any at the city level. In person surveys will be done in Agra, Jaipur

For phone surveys, we designed a sample of 2000 complete surveys. Moreover, over sampling will be done in Rajasthan, Uttar Pradesh and Delhi to ensure at least 50 interviews in each city. This sample is designed such that we can conduct descriptive analysis for 3-4 sub-groups (say by cities or by socio-economic categories) with at least 300-400 sample in

each sub-group. The purpose of phone surveys will be to add more statistical power to limited in-person sample size we have for few key questions of interest.

We also expect that the phone surveys and in-person data will be used for statistical group mean tests between regular users and one-time or non-users to compare SRH and ANC related practices between the two groups. It is not a controlled trial of Tiko platform but will be exploratory to understand additionality in service usage of regular users if any.

Assuming at least 150 regular and 150 non-users included in the in-person surveys, the sample will have power to detect 25% relative change or 0.25 SD change from an outcome distributed binomially with mean of 0.50 or with standardized normal distribution with mean 0 and SD of 1 N $^{\circ}(0,1)$  with power of 80% and Type I error of 0.10 with one sided test.

Assuming 500 regular and 500 non-users included in the in-person surveys, the sample will have power to detect 15% relative change or 0.15 SD change from an outcome distributed binomially with mean of 0.50 or with standardized normal distribution with mean 0 and SD of 1 N~(0,1) with power of 80% and Type I error of 0.10 with one sided test.

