#### 2.3 Sampling for In-Person and Phone-Surveys

The sample frame for both surveys will be the Tiko beneficiary database available with Triggerise. Below is the summary of viable database sample frame (exclude smaller sites where the programme is too small to be considered in this study)

Stata	City	Area	Number of		
Sidle			Enrollments	Actual Users	Non-Users
Uttar Pradesh	Agra	Both	34,726	21,743	12,983
Rajasthan	Jaipur	Both	29,588	28,531	1,057
Rajasthan	Ajmer	Urban	7,325	4,532	2,793
Rajasthan	Tonk	Peri Urban	5,176	3,993	1,183
Delhi	Delhi	Urban	3,846	3,142	704
Uttar Pradesh	Firozabad	Peri Urban	1,044	119	925
TOTAL			81,705	62,060	19,645

The following steps will be followed for sampling of in-person survey respondents:

- 1. Restrict the study to only Jaipur and Agra which constitutes 70% of the enrollments and 84% of the actual user base.
- 2. Stratify sample as 150 non-users (enrollment minus users) and 350 users
- 3. Distribute sample in approx. proportion to the actual numbers in both cities for users and non-users as below.

City	Non-users	Actual Users	Total
Agra	100	150	250
Jaipur	50	200	250
Total	150	350	500

- 4. Distribute the sample across the 'Tiko Pro Agents' working in the city. We currently don't have this data, but we expect to complete at least 5 interviews per agent and spread the sample to cover about 25% of the agents working in the city.
- 5. Based on above, randomly sample the Pro Agents from database that will be made available by Triggerise.
- 6. Obtain a list of randomly sampled Beneficiaries from Triggerise for each sampled pro agent. We will obtain 3-times the number of completed interviews required per agent because our scoping visit suggests expecting 30-40% response rate in finding the beneficiary house with help of agent and then getting their consent for the interview. If required, Triggerise will make available more beneficiaries (their name and phone numbers per agent) if the sample size is not achieved.
- 7. NEERMAN enumerators will call each beneficiary sequentially in the list and fix appointments for the in-person interview. The phone records will track validity of numbers, refusals, and consents. Pro agent's help will be sought to find address or in field logistics or to establish our enumerators' bona fides.

The following steps will be followed for sampling of phone-survey respondents:

- 1. Exclude Firozabad which has no programme in 2020

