- 2. Stratify sample as 500 non-users (enrollment minus users) and 1500 users
- 3. Distribute sample in proportion to the actual numbers as below.

City	Non-users	Actual Users	Total
Agra	347	527	873
Jaipur	28	691	719
Ajmer	75	110	184
Tonk	32	97	128
Delhi	19	76	95
Total	500	1500	2000

- 4. Obtain a list of randomly sampled Beneficiaries as above. We will obtain 10-times the number of completed interviews required per agent because our scoping visit suggests to expect 10-15% response rate in phone surveys. If required, Triggerise will make available more beneficiaries (their name and phone numbers per agent) if the sample size is not achieved.
- 5. NEERMAN enumerators will call each beneficiary sequentially in the list and fix appointments for the phone interview. The phone records will track validity of numbers, refusals and consents. Pro agent's help will be sought to establish our enumerators' bona fides if needed.

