#### 2.6 Quantitative Data Quality Assurance, Processing and Analysis

We would conduct 20% centralised back-checks over phone to ensure in-person visits actually happened and cross-check factual data. For phone surveys, 20% audio- listening-in checks by the coordinator/monitor will be done to cross-verify the factual data. Apart from this, thorough back-office data quality checks (outliers, straight line responses, etc) will be done on pre-identified important variables. A researcher will ensure accuracy of data every third day of the survey by using high-frequency data quality checks for quantitative surveys.

Quantitative data will be entered in a CAPI App on ODK system, transmitted to secure server with 16-key encryption, and downloaded to a dedicated desktop for data. The data will be deidentified immediately first. Second, the processing will include giving variable and value labels, removing duplicate submissions if any, coding open ended responses if they exceed 5% of any categorical question's answers, etc. Then, this de-identified and processed data is submitted to researchers for further analysis in STATA format.

We mainly anticipate descriptive analysis to tabulate indicators related to knowledge, practices, barriers, enablers w.r.t. SRH and MCH services, exposure and use of Tiko platform, how it has helped or not helped or affected their well-being, suggestions and preferences for different components of the platform, etc. We anticipate cross tabulation by socio-economic characteristics, regions (say by Cities), and duration of use.

While no analytical tests are anticipated at this time, we expect to conduct standard bivariate tests (t-test and chi2 test) and regression analysis for more nuanced group mean tests or multiple comparison tests (logit, OLS, mixed models). We will be adjusting for

standard errors for robust inference. In case of statistical inference, we expect one side test with alpha < 0.1 to consider a relationship or test statistic significant.

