## 3 Ethics and Protection of Research Participants

This research is socio-economic-health impact assessment of a private mHealth platform. There is no drug, intervention or device being tested. The platform simply connects users to service providers and products available as per existing government rules and approvals already. So, it is basically a study of how a 'market place' actually helps beneficiaries?

Overall, the research should merit expedited IRB review. However, below is our assessment of risks and benefits to the participants.

**Interview of Tiko Users** – the platform users' age ranges from 18 years to 45 years. The qualitative IDIs or field visits include discussion with a few users about the practices, knowledge, benefits, barriers or contexts of users interviews. However, the quantitative surveys will be conducted of similar Tiko platform users. For all the respondents written consent will be administered and recorded.

**Uneasy questions** – Some of the questions related to contraceptives, pregnancy, family planning can be perceived as private. The respondent has a right to refuse answer to such and any questions. The interviews are also conducted by female interviewers in privacy. The consent form will specifically mention this risk and their right to refuse.

**Data privacy and security** – Qualitative interviews will be audio recorded along with notes, quantitative interviews will be conducted using CAPI/CATI apps, and both interviews will collect identifiable information such as name and phone number for survey management purposes only. These variables will be used in case of repeat visits and back checks of data only. We will also collect GPS coordinates purely to track movement of enumerators in field surveys but this data will not be linked to individual respondents.

Qualitative interviews/discussions will record name and phone numbers only in a diary and use a pseudo name (Rafiki, Doc, Bhai, etc) and never real name in the conversation once the audio recording starts. The case narrative for each interview will be written up within 3 days of the interview. After study conclusion all audio files will be deleted after 3 months period along with diaries which can link audio recordings to specific respondents. All this data will be controlled by a single person on non-networked computer.

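### Section 2.3 describes the in-person non-user allocation (100 Agra, 50 Jaipur) as roughly proportional, but the frame gives 139 and 11; the 70% and 84% coverage figures are also wrong

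*Protocol*

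**What the plan says.** Protocol section 2.3 prints a frame of enrolments, users and non-users by city. The Agra row reads "34,726 21,743 12,983"; the Jaipur row has 29,588, 28,531 and 1,057 in the same order.

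For the in-person survey, step 1 is: "Restrict the study to only Jaipur and Agra which constitutes 70% of the enrollments and 84% of the actual user base". Step 2 fixes 150 non-users and 350 users. Step 3 is: "Distribute sample in approx. proportion to the actual numbers in both cities for users and non-users as below". The table under step 3 gives 100 non-users and 150 users in Agra, and 50 non-users and 200 users in Jaipur, so each city totals 250.

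The phone survey has a parallel instruction, "Distribute sample in proportion to the actual numbers as below", with its own table for five cities.

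On analysis, section 2.6 says "We anticipate cross tabulation by socio-economic characteristics" and also foresees tables by city. It does not say whether estimates pooled over cities will be weighted.

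**The concern.** Agra has about twelve times as many non-users as Jaipur (12,983 / 1,057 = 12.3), yet the table gives it only twice as many non-user interviews. That cannot follow from a proportional rule, even an approximate one. The two coverage percentages in step 1 also disagree with the frame printed just above them.

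The study is mainly descriptive, so the meaning of a pooled percentage depends on how each cell was sampled. A reader who takes step 3 at its word will treat the non-user sample as self-weighting by city and see no need for a city weight. Any non-user figure pooled over the two cities, whether overall or by socio-economic group, would then describe a population in which Jaipur counts for far more than it does in the frame.

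**Working it through.** **Inputs** (all from section 2.3). Non-users: Agra 12,983, Jaipur 1,057, sum 14,040. Users: Agra 21,743, Jaipur 28,531, sum 50,274. Enrolments: 34,726 + 29,588 = 64,314. Frame totals: 81,705 enrolments, 62,060 users, 19,645 non-users. In every row, enrolments minus users equals non-users, and the columns add to the printed totals, so the frame is internally sound.

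**Proportional allocation**, n(city) = n(stratum) × N(city) / N(two cities):

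| Cell | Formula | Proportional | Printed |
|---|---|---|---|
| Users, Agra | 350 × 21,743 / 50,274 | 151.4 | 150 |
| Users, Jaipur | 350 × 28,531 / 50,274 | 198.6 | 200 |
| Non-users, Agra | 150 × 12,983 / 14,040 | 138.7 | 100 |
| Non-users, Jaipur | 150 × 1,057 / 14,040 | 11.3 | 50 |

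The user row reproduces. The non-user row is off by 39 interviews. The phone table follows its rule in all ten city cells to within rounding; for example, without Firozabad, 500 × 12,983 / 18,720 = 346.8 (printed 347) and 500 × 1,057 / 18,720 = 28.2 (printed 28).

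Neither alternative rule tried explains the row. State totals give about 110 and 40 non-users, but then 130 and 220 users. Square-root allocation gives 117 and 33.

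**Sampling rates.** Non-users: 100 / 12,983 = 0.770% and 50 / 1,057 = 4.730%, ratio 6.14. Users: 150 / 21,743 = 0.690% and 200 / 28,531 = 0.701%, ratio 1.02.

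**Shift in an unweighted pooled non-user estimate.** Jaipur's weight is 50 / 150 = 0.333 instead of 1,057 / 14,040 = 0.075, an excess of 0.258. The document gives no city difference, so a range is assumed:

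| Assumed Jaipur minus Agra (pp) | 5 | 10 | 20 | 30 |
|---|---|---|---|---|
| Shift (pp) | 1.3 | 2.6 | 5.2 | 7.7 |

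**Cost of weighting.** The weights are 12,983 / 100 = 129.8 and 1,057 / 50 = 21.1. The Kish factor is 150 × Σ(n w²) / (Σ n w)² = 1.30, so the effective n is 150 / 1.30 = 115. At p = 0.5 the standard error is 4.08 pp unweighted and 4.65 pp weighted; the 95% half-widths are 8.0 and 9.1 pp. Weighting lowers mean squared error once the bias exceeds √(4.65² − 4.08²) = 2.23 pp, that is, once the cities differ by more than 2.23 / 0.258 ≈ 8.7 pp.

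**Precision by city**, 1.96 × √(0.25 / n): 9.8 pp for n = 100, 13.9 pp for n = 50, and about 29 pp for the 11 Jaipur interviews that proportionality would give.

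**Coverage in step 1.** Enrolments: 64,314 / 81,705 = 78.7% (stated 70%). Users: 50,274 / 62,060 = 81.0% (stated 84%). Non-users: 14,040 / 19,645 = 71.5%. Without Firozabad: 64,314 / 80,661 = 79.7% and 50,274 / 61,941 = 81.2%. No combination of one to five cities yields the stated pair.

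**The case against.** The strongest reply is that the harm is conditional and the design itself is sensible.

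- **Size.** The shift needs a pooled two-city figure, no weights and a real city difference. It equals the 8.0 pp half-width only when the cities differ by about 31 pp (8.0 / 0.258). This stands; the size is conditional.
- **Visibility.** Both tables are printed, so a careful reader can see that the row is not proportional. City tables are planned and are not affected. Step 2 already over-represents non-users (30% of the sample against 14,040 / 64,314 = 21.8% of the two-city frame), so some weighting would be needed anyway, and its detail may sit in an analysis plan. All true. But a weight for user status does not correct the city mix within non-users, and step 3 tells the analyst that no such correction is needed.
- **Weighting is not free.** Below a city difference of about 8.7 pp it raises mean squared error. Applying the section 2.2 design effect of 1.25 (an assumption here) moves that point to 8.7 × √1.25 ≈ 9.7 pp. This stands, and is a reason to make the city tables the main report.
- **The departure helps the user comparison.** The gap in Jaipur share between all users and non-users is 200/350 − 50/150 = 24 points as printed, against 28,531/50,274 − 1,057/14,040 = 49 points under proportionality. City-adjusted information is 150×100/250 + 200×50/250 = 100 units, against 151.4×138.7/290.1 + 198.6×11.3/209.9 = 83. This also stands. It supports keeping the numbers, not the description.
- **Perhaps the oversample was intended.** The equal city totals of 250 suggest so. Yet the only oversampling sentence, in section 2.2, belongs to the phone survey and sets a minimum per city, which Jaipur's 250 interviews meet without it.

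**Conclusion.** The concern holds. Section 2.3 contradicts its own frame in two places.

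The more important one is the in-person non-user row: 100 and 50 are printed under a proportional rule that gives 139 and 11. The word *approx.* covers the user row, which is off by one or two interviews, but not this one. An unweighted pooled non-user estimate would be biased towards Jaipur by 0.258 times the city difference. That size rests on the printed frame counts and target sample sizes; the bias is zero if the cities do not differ. The protocol does not commit to unweighted pooling, so the established error is that the allocation is described wrongly. User figures and city-specific tables are untouched.

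The coverage figures in step 1 are a plain error with no consequence for the design, since 79% and 81% still support restricting the survey to Agra and Jaipur.

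**What to change.** 1. Keep 100 and 50. State in step 3 that the non-user allocation is deliberately disproportionate, so that Jaipur non-users can be reported in their own table.
2. Report non-user results by city. Where a pooled two-city figure is given, weight each city by its eligible frame count divided by its completed interviews. On the printed counts the weights are about 130 (Agra) and 21 (Jaipur). Section 2.2 says "of which we expect to complete 480 interviews"; if those fall pro rata (assumption: 96 and 48 non-users), the weights are about 135 and 22.
3. Treat these weights as provisional. Section 2.1 says: "The survey participants will be women (18-35years of age) who had subscribed to Tiko card between 2018 and 2020". Section 3 says platform users' "age ranges from 18 years to 45 years". The printed frame may therefore include women who are not eligible. Final weights need the age-eligible count per city, the actual completes and the record of agent-level selection.
4. Correct step 1 to 79% of enrolments and 81% of users.
5. Separately, and not because of this error, include city as a term or stratum in comparisons of users with non-users, because the frame itself makes the groups differ by city. The split of regular users by city is not given, so the imbalance for the regular-user contrast in section 2.2 cannot be computed.

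The cost is two sentences of protocol wording and no change to fieldwork. Weighted pooled non-user figures lose precision by a factor of about 1.30 in variance: effective n about 115 of 150, or 144 / 1.30 ≈ 111 of 144 at 480 completes. The eligible counts must come from the sponsor's database. Reporting by city needs no weight for the city allocation.

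### In-person survey: Pro Agents are drawn with no stated regard to caseload and only a floor of five interviews each, so unweighted percentages may over-represent women of small agents

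*Protocol*

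**What the plan says.** Section 2.3 of the protocol limits the in-person survey to Agra and Jaipur and fixes the numbers by user status: "Stratify sample as 150 non-users (enrollment minus users) and 350 users". Step 3 spreads these over the two cities roughly in line with the actual numbers.

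The agent stage follows. Step 4 says of the agent-level information "We currently don't have this data", and then that "we expect to complete at least 5 interviews per agent and spread the sample to cover about 25% of the agents". Step 5 is to "randomly sample the Pro Agents from database that will be made available by Triggerise". Step 6 is to "Obtain a list of randomly sampled Beneficiaries from Triggerise for each sampled pro agent", with the list size set as follows: "We will obtain 3-times the number of completed interviews required per agent". How the required number is set for a given agent is not stated.

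The planned precision in section 2.2 comes from "measuring a proportion of 50% with 5 pp error rate and 95% confidence which yields n of 384", "increased by design effect of 1.25 to account for clustering if any at the city level". Sections 2.1 and 2.6 plan mainly descriptive tables, some tests and regressions, and adjusted standard errors.

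**The concern.** This is a two-stage sample in which the agent is the first-stage unit. If agents are drawn with equal probability and each supplies about the same number of women, a woman's chance of inclusion is inversely proportional to her agent's caseload. The unweighted percentage then estimates the plain average of agent-level percentages, not the percentage among beneficiaries. That would undo, within each city, the proportionality sought in step 3.

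The two differ when caseload is related to the outcome. Agents with many clients might follow women up more or less closely than agents with few, and that could show in regular use, contraceptive practice or satisfaction. The protocol has no data on this either way. Adjusted standard errors would not help, because they change the interval and not the point estimate. The 1.25 design effect is a variance allowance at city level and does not address selection by agent.

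Timing matters. The draw and the take happen before any analysis, and later weighting is possible only if each sampled agent's caseload was recorded. Step 6 asks for lists of women, not for agent totals.

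**Working it through.** **Inputs from the protocol.** Section 2.2: proportion 50%, margin 5 points, 95% confidence, n = 384, design effect 1.25, 480 completes. Section 2.3: 34,726 enrolled in Agra and 29,588 in Jaipur, together 64,314; 500 in-person interviews allocated; at least 5 per agent; about 25% of agents.

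**Inputs not in the protocol, assumed.** Coefficient of variation (CV) of caseload, 0 to 1.0; correlation rho between caseload and the agent-level percentage; between-agent SD of that percentage. An SD of 15.8 points means that 10% of the variance of a 50% indicator lies between agents (0.158² / 0.25 = 0.10).

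**1. The plan's own figure.** n = 1.95996² x 0.25 / 0.05² = 384.1, and 384.1 x 1.25 = 480.2. The 480 reproduces. It contains no term for the agent stage.

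**2. Scale implied at the floor.** 500 / 5 = 100 sampled agents; 100 / 0.25 = 400 agents; 64,314 / 400 = 161 enrolled women per agent on average. With 10 interviews per agent, this becomes 50 sampled, 200 in all and about 322 women each.

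**3. Chance of selection under equal probability and equal take.** For caseload M it is 0.25 x 5 / M. At M = 161 this is 0.78%, which agrees with 500 / 64,314 = 0.78%. At M = 80 it is 1.56% and at M = 240 it is 0.52%, a ratio of 3. Because users and non-users have separate quotas, M within a stratum is the agent's count of users or of non-users. The reasoning is the same.

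**4. Bias.** The unweighted mean estimates the simple average of the agent percentages; the target weights them by M. The difference is -Cov(M, agent percentage) / mean(M) = -rho x CV x between-agent SD. Its sign depends on rho; its size is |rho| x CV x SD.

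**5. Range.** The smaller half of agents supplies 50% of the interviews. Its share of women was simulated with lognormal caseloads for CV above 0; at CV 0 it is 50% by definition.

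| CV of caseload | Women under the smaller half of agents | Bias, rho 0.3, SD 15.8 points | Kish factor 1 + CV² |
|---|---|---|---|
| 0 | 50% | 0 | 1.00 |
| 0.25 | 40% | 1.2 points | 1.06 |
| 0.5 | 32% | 2.4 points | 1.25 |
| 1.0 | 20% | 4.7 points | 2.00 |

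For CV 0.25, 0.5 and 1.0 at rho 0.3, an SD of 10 points gives 0.75, 1.5 and 3.0 points, and an SD of 22 points gives 1.65, 3.3 and 6.6. With rho = 0 the bias is zero at every CV.

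**6. Price of repairing by weights.** With 480 completes, the 95% margin from weighting alone is 1.96 x sqrt(0.25 x K / 480). This is 4.6 points at K = 1.06, 5.0 at K = 1.25 and 6.3 at K = 2.00, before any clustering by agent.

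**The case against.** The strongest reply is that the protocol leaves the agent stage open and does not fix it wrongly. Five is a minimum. Step 6 speaks of a required number per agent, which may differ between agents. A take proportional to caseload fits those words, follows naturally from step 3, and would be self-weighting within stratum. Step 5 says random, and a size-proportional draw is also random. Weights may sit in an analysis plan that is not shown, so their absence from the protocol is no fault. The study is described as descriptive and exploratory, and in comparisons of users with non-users a distortion shared by both groups may partly cancel.

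Most of this stands, and it limits the point. Equal take is the natural reading, because five is the only number given, but it is still an inference. So are unequal caseloads.

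A reader might go further and infer that the pooled estimates do not describe the beneficiaries, or that the bias exceeds the 5-point margin. The documents do not support either. Suppose half the agents have 100 clients and half have 500, with an indicator at 60% and 40% respectively. The survey would report 50% against a true 43.3%, a bias of 6.7 points. But that example assumes a perfect correlation (1 x 0.667 x 10 points). With rho = 0.3 and the rest unchanged the bias is 2.0 points, and with rho = 0 it is zero. The example also does not fit five interviews per agent: a mean of 300 clients implies about 64,314 / 300 = 214 agents, a quarter is about 54, and 500 / 54 is about 9 each.

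What the reply does not remove is the order of events. An analysis plan cannot recover selection probabilities if the caseloads were never collected, and no sentence in section 2.3 excludes the unfavourable reading.

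**Conclusion.** The point holds in conditional form. Section 2.3 draws agents with no stated regard to caseload and sets only a floor for the take. If caseloads differ and the take is about equal, women of small agents are over-represented within each city and user stratum, and unweighted in-person percentages may not represent the beneficiaries.

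Bias in an estimate requires all of the following: unequal caseloads, a roughly equal take, outcomes that vary with caseload, and no weighting. The protocol establishes none of the first three. On the stated assumptions (rho 0.3, SD about 16 points) the bias is about 1 to 5 points for a CV of 0.25 to 1.0. At the upper end that is similar to the planned margin. Larger or smaller values follow from other assumptions, and nothing in the protocol chooses between them. The point concerns the in-person survey only: the phone sample is allocated by city and user status, without a stage that samples agents. It is worth correcting because the remedy is cheap and must precede fieldwork.

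**What to change.** In step 5, state that agents are drawn within city with probability proportional to their number of enrolled beneficiaries, and in step 4 that an equal number is taken from each. This is self-weighting within a stratum to the extent that agents have a similar mix of users and non-users. Separate size measures for users and non-users would be more exact, at the price of two counts and possibly two sets of agents.

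Alternatively, keep the simple random draw and do one of two things:

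- make the take proportional to caseload; or
- obtain each sampled agent's user and non-user counts with the step 6 list, and weight by the inverse of the selection probability.

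The cost is a sentence or two in section 2.3 and a count per agent from the database holder: for all agents under the size-proportional draw, for the sampled agents under weighting. The planned total of interviews does not change. Very large agents may be selected with certainty and then need more interviews than the others. If weighting is used, it costs precision by a Kish factor of about 1 + CV².

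### Phone step 4 draws names through agents, although the phone allocation has no agent stage; as written this clusters a centrally dialled survey for no travel saving and with no design effect

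*Protocol*

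**What the plan says.** All of the selection text is in Protocol Section 2.3.

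- **Phone steps 1 to 3.** Firozabad is dropped. Step 2 reads "Stratify sample as 500 non-users (enrollment minus users) and 1500 users" and step 3 "Distribute sample in proportion to the actual numbers as below". The table that follows has cells for city and user status only, for example "Agra 347 527 873" and "Jaipur 28 691 719" (non-users, users, total). Agents do not appear.
- **Phone step 4.** "Obtain a list of randomly sampled Beneficiaries as above", followed by "We will obtain 10-times the number of completed interviews required per agent". The reason given is that "our scoping visit suggests to expect 10-15% response rate in phone surveys". Further names can be requested, again per agent.
- **What stands above.** The only earlier procedure is the in-person one, which is restricted to Agra and Jaipur. It aims for at least 5 completed interviews per agent and about a quarter of each city's agents, samples agents at random, and then says "Obtain a list of randomly sampled Beneficiaries from Triggerise for each sampled pro agent". It also states that the agent data are not yet held.

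Section 4 places the phone interviewers in a Delhi/Mumbai office. Section 2.2 applies a design effect of 1.25 to the in-person sample size, for clustering at city level. It states none for the 2,000 phone interviews or for the 500 v 500 power statement.

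**The concern.** Step 4 does not fit the three steps before it. It calls for a number of interviews per agent that the phone allocation never sets, and it points back to an agent sample that does not exist for Ajmer, Tonk and Delhi. Whoever draws the list must either invent an agent stage or ignore the words.

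If the words are followed, the phone survey inherits a cluster stage whose usual justification is field travel, and a survey dialled from an office has none. Once the agents are drawn, women attached to the others cannot be called. With a random draw of agents this need not bias the estimates, but it concentrates interviews and costs precision. The phone survey is meant to add statistical power on key questions, so an unplanned loss of precision works against its purpose. A restricted pool could also run short of non-users, the smaller stratum.

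**Working it through.** **1. The plan's allocation.** Without Firozabad the frame has 18,720 non-users and 61,941 users. Agra non-users: 500 × 12,983 / 18,720 = 346.8 (table 347). Jaipur users: 1,500 × 28,531 / 61,941 = 690.9 (table 691). The other cells also reproduce. The allocation is therefore proportional within user status, with no agent term. The rounded cells sum to 501 and 1,501, which is only rounding.

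**2. Supply of non-users.** Two assumptions: the in-person figure of about 25% of agents carries over to every phone city, and those agents hold 25% of each city's non-users. For Ajmer, Tonk and Delhi this also supposes a fresh draw of agents, which the protocol does not describe.

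| City | Ten-times list | 25% of non-users | List as share of all non-users |
|---|---|---|---|
| Agra | 3,470 | 3,246 | 26.7% |
| Jaipur | 280 | 264 | 26.5% |
| Ajmer | 750 | 698 | 26.9% |
| Tonk | 320 | 296 | 27.0% |
| Delhi | 190 | 176 | 27.0% |

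Overall: 500 × 10 = 5,000 names needed, and 0.25 × 18,720 = 4,680 available. The shortfall is 320 / 5,000 = 6.4%. The user lists fit, at about 24% of the frame in each city.

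The quota counts completed interviews, not names. The 4,680 names yield 468 at 10% response, 585 at 12.5% and 702 at 15%. Break-even is 500 / 4,680 = 10.7%.

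**3. Interviews per agent.** In person, 250 interviews per city at 5 or more per agent means at most 250 / 5 = 50 agents. If the same agents serve the phone survey, each Agra agent carries at least 873 / 50 = 17.5 phone interviews and each Jaipur agent at least 719 / 50 = 14.4. Jaipur's 28 non-users spread over 50 agents would be fewer than one each.

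**4. Precision of an overall Agra estimate.** DEFF = 1 + (m − 1) × ICC with m = 17.46. At ICC 0.02 it is 1 + 16.46 × 0.02 = 1.33; at ICC 0.0625 it is 2.03. Both ICCs are assumed. The second is the value at which 5 interviews per agent give 1.25 (1 + 4 × 0.0625). The protocol's 1.25 is for cities, so it does not establish an agent-level ICC.

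**5. Power for 500 v 500.** Difference 0.15 SD, one-sided 0.10, critical value 1.2816.

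- *No clustering:* SE = √(2/500) = 0.0632; 0.15 / 0.0632 − 1.2816 = 1.090; power 86%. For 80% power 401 per group suffice, so the plan's statement holds and leaves room for a design effect of about 500 / 401 = 1.25.
- *Agent effects that do not cancel:* cluster size is counted within group. Agra non-users 347 / 50 = 6.94, users 527 / 50 = 10.54.
  - ICC 0.02: DEFF 1.119 and 1.191; SE = √((1.119 + 1.191)/500) = 0.0680; power 82%.
  - ICC 0.0625: DEFF 1.371 and 1.596; SE = √((1.371 + 1.596)/500) = 0.0770; power 75%.
- *Agent effects shared by both groups, balanced within agent:* the variance becomes 2(1 − ICC)/500. Power is 87% at ICC 0.02 and 88% at 0.0625, so nothing is lost.

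These figures apply Agra's cluster sizes to the whole contrast.

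**The case against.** The strongest reply is that step 4 is only loosely worded. *Per agent* may describe how the database supplies names, not a sampling stage. The 25% is stated only for the in-person survey, as an approximate figure, and before the agent data were available; coverage of about 27% would remove the list shortfall. Step 4 also allows more names to be requested, and step 5 lets agents vouch for the interviewers, which has value at 10-15% response. The study calls itself mainly descriptive and exploratory, and robust standard errors are foreseen.

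Much of this stands, and it limits the size of the point. It does not make step 4 executable: no reading of its words yields a phone quota per agent, or a list of agents outside Agra and Jaipur. Robust standard errors would report a precision loss, not prevent it. The vouching role needs only that each woman's agent be known.

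Two stronger readings are tempting and are not supported. A reader might infer that the sampled agents *cannot* supply the 500 non-users. Under the carry-over assumptions the shortage is one of listed names, and the quota is missed only at the bottom of the stated response range. Jaipur would fail across that range (114 names, 11 to 17 completes against 28) only if the 150 names listed for the in-person survey were barred from the phone list, which the protocol does not say. A reader might also put the pooled Agra cluster size of 17.5 into the 500 v 500 comparison and obtain power of about 78% (ICC 0.02) or 65% (ICC 0.0625). That counts both groups in each cluster and ignores that shared agent effects largely cancel in a contrast between users and non-users.

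**Conclusion.** The point holds as a defect in the selection rule. Step 4 brings in an agent stage that steps 1 to 3 do not contain, that is undefined for three of the five cities, that saves no travel, and for which no design effect is allowed.

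Its size is moderate and conditional. The list shortfall is about 6%, resting on the carried-over 25% and an even spread of women across agents; the quota is at risk only below about 10.7% response. Overall Agra estimates would carry a design effect of about 1.33 or more at an assumed ICC of 0.02 if the in-person agents are reused. The 500 v 500 contrast would have between 75% and 82% power if agent effects do not cancel, and about the unclustered 86% if they do. The number of agents, the spread of women across them and the ICC are not given, so none of these figures can be narrowed from the document.

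**What to change.** Rewrite phone step 4 so that names are drawn by simple random sampling directly from each full city-by-user-status list, with no agent stage. Delete *as above* and *per agent*, in the top-up sentence too, so that extra names come from the same lists. Record each woman's agent as a variable, so that the agent can still vouch for the interviewer when needed.

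The ten-times lists then need only about 27% of the non-users in each city, so the frame suffices everywhere. The cost is a change of wording and one database draw, with no extra interviews. The small downside is that more agents may have to be contacted for help with introductions.
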